The endoscopic subscore result from the central reader during the screening period will be used to evaluate the eligibility of a subject to enroll in the study and for all efficacy assessments at Week 8 of Part 1. However, for re randomization into Substudy 3, the endoscopic subscore at Week 8 (Study M14-675 Part 1) or Week 16 (Study M14-675 Part 2) based on the local reader's assessment will be used to determine clinical response status compared to the Baseline assessment of the central reader for enrollment into Study M14-234 Substudy 3.

In addition to the Mayo endoscopic subscore, the central reader will assess the endoscopy findings using the Ulcerative Colitis Endoscopic Index of Severity (UCEIS) scoring system for additional exploratory analyses. Blood samples will be collected for high sensitivity C-reactive protein (hs-CRP), upadacitinib plasma concentrations and other biomarker analyses. In addition, stool samples for fecal calprotectin will be collected. The stool samples should be taken before starting bowel preparations for scheduled endoscopies.

Subjects will be asked to fill out the Inflammatory Bowel Disease Questionnaire (IBDQ), Work Productivity and Activity Impairment (WPAI), European Quality of Life 5 Dimensions 5 Levels (EQ-5D-5L), Short Form 36 Item (SF-36), and Functional Assessment of Chronic Illness Therapy-Fatigue (FACIT-F), Ulcerative Colitis Symptoms Questionnaire (UC-SQ), and Patient Global Impression of Severity (PGIS; only in select sites) during the study at Baseline, Week 2, and Week 8/PD for Part 1. These same questionnaires will be completed at Week 16/PD for Part 2.

Methodology (Continued):

Subjects will be asked to fill out the Patient Global Impression of Change (PGIC) during the study at Week 2, and Week 8/PD for Part 1. This same questionnaire will be completed at Week 16/PD for Part 2. During each study visit subjects will also be asked to report UC-related hospitalizations and surgeries which will be captured as a part of the supplemental Health Care Resource Utilization (HCRU) form of Adverse Event collection in electronic data capture.

Subjects will be discontinued from the study if they withdraw consent or if they are deemed unsuitable to continue for any reason by the investigator.

Washout Period:

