## 3.2 Secondary Endpoints

The ranked secondary efficacy endpoints for Part 1 under overall type I error control are as follows:

[figure not shown]
- 1. The achievement of endoscopic improvement at Week 8;
- 2. The achievement of endoscopic remission at Week 8;
- 3. The achievement of clinical response per Adapted Mayo score at Week 8;
- 4. The achievement of clinical response per Partial Adapted Mayo score at Week 2;
- 5. The achievement of histologic-endoscopic mucosal improvement at Week 8;
- 6. The achievement of no bowel urgency at Week 8;
- 7. The achievement of no abdominal pain at Week 8;
- 8. The achievement of histologic improvement at Week 8;
- 9. Change from Baseline in IBDQ total score at Week 8;
- 10. The achievement of mucosal healing at Week 8;
- 11. Change from Baseline in FACIT-F score at Week 8.

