#### 8.3.2 Continuous Endpoints

For continuous endpoints, missing data will be handled using Mixed-Effect Model Repeat Measurement (MMRM).

The MMRM will be conducted using mixed model including observed measurements at all visits, except that measurements at or after the occurrence of UC-related corticosteroids intercurrent event will be excluded (see Section 8.2.2). The mixed model includes the categorical fixed effects of treatment, visit and treatment-by-visit interaction, randomization stratification factors (bio-IR status [bio-IR vs. non-bio-IR], Baseline corticosteroid use [yes vs. no] and Baseline Adapted Mayo score [≤ 7 vs. > 7]), and the continuous fixed covariates of Baseline measurements. An unstructured variance covariance matrix (UN) will be used. If the model cannot converge, an autoregressive (1) or compound symmetric (CS) covariance structure matrix will be used. The parameter estimations are based on the method of restrictive maximum likelihood (REML). The fixed effects will be used to report model-based means at corresponding visits.

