#### 8.5.1 Key Secondary Efficacy Analyses

The key secondary endpoints are defined in Section 3.2. The estimands corresponding to the secondary efficacy endpoints are defined in Section 2.1. Details of the estimand definitions are outlined in Appendix E. For ITT1 Population, secondary efficacy endpoints in Part 1 will be analyzed by comparing upadacitinib treatment group and placebo group. The binary secondary endpoints will be analyzed by CMH and the corresponding analyses are specified in Section 8.3.1. The NRI-C will be the primary approach for missing data handling in the analyses of binary secondary efficacy endpoints. The NRI-NC approach will be used as sensitivity analyses.

The continuous secondary endpoints will be analyzed by MMRM and the corresponding analyses are specified in Section 8.3.2.

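### The MMRM for IBDQ and FACIT-F shares one Baseline slope across Week 2 and Week 8; a Baseline-by-visit term would protect Week 8 precision at almost no cost

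*SAP*

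**What the plan says.** SAP 3.2 ranks "Change from Baseline in IBDQ total score at Week 8" ninth and "Change from Baseline in FACIT-F score at Week 8" eleventh. SAP 8.5.1 sends both to the repeated-measures model: "The continuous secondary endpoints will be analyzed by MMRM and the corresponding analyses are specified in Section 8.3.2".

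On the fixed effects, SAP 8.3.2 states: "The mixed model includes the categorical fixed effects of treatment, visit and treatment-by-visit interaction". It then adds the three stratification factors "and the continuous fixed covariates of Baseline measurements". On the covariance it states: "An unstructured variance covariance matrix (UN) will be used". Estimation is by REML, with an autoregressive or compound-symmetric structure as fallback if the model does not converge. Treatment-by-visit is the only by-visit interaction listed, and no other SAP section adds one for Baseline.

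The Protocol synopsis schedules the questionnaires "during the study at Baseline, Week 2, and Week 8/PD for Part 1", so the model has two post-baseline visits. SAP 3.3 also lists both scores as endpoints over time. SAP 8.1 reserves ANCOVA for variables with a single post-baseline visit.

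**The concern.** With a main effect only, the relation between the Baseline score and later change is forced to be the same at Week 2 and Week 8. The fitted common slope is a weighted mean of the two true slopes. When Week 2 is the less variable visit, it carries most of the weight. The only tested visit, Week 8, would then be adjusted mainly with the slope that belongs to Week 2.

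If the slopes differ, part of the Baseline information about Week 8 stays in the residual, and the Week 8 standard error is larger than it need be. Testing is fixed-sequence (SAP 12.0), so a miss on IBDQ at rank 9 would also stop formal testing of mucosal healing (10) and FACIT-F (11).

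**Working it through.** **Plan's own figure.** The documents give no precision or power for IBDQ or FACIT-F. The only power statement (SAP 2.4) concerns remission: 5% vs 18%, 154 vs 308 subjects, two-sided Fisher's exact test at 0.05, power above 95%. Exact enumeration gives 98.9%, so that figure is reproduced, but it does not bear on this point.

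**Inputs.** From the documents: arms of 308 and 154, two post-baseline visits, the fixed effects and covariance above. Everything else is assumed. The visit schedule is taken from the synopsis because the questionnaire row of Appendix C could not be read reliably in the text available.

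**Formula (large sample, complete data).** Let S be the within-arm covariance of the Week 2 and Week 8 changes given Baseline, b2 and b8 the true Baseline slopes, and sd0 the Baseline SD.

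- Weight of Week 2 in the common slope: w2 = (S88 − S28) / (S22 + S88 − 2·S28)
- Common slope: b = w2·b2 + (1 − w2)·b8
- Proportional increase in the Week 8 treatment-effect variance: (b8 − b)² · sd0² / S88, where b8 − b = w2·(b8 − b2)

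**Set 1: points on an IBDQ-like scale.** Baseline SD 35; residual SDs 26 (Week 2) and 34 (Week 8); residual correlation 0.5.

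- S22 = 676, S88 = 1156, S28 = 0.5 × 26 × 34 = 442
- w2 = (1156 − 442) / (676 + 1156 − 884) = 714 / 948 = 0.753
- Gap 0.2: (0.753 × 0.2)² × 1225 / 1156 = 2.4%. Gap 0.3: 5.4%. Gap 0.4: 9.6%.

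With a Week 2 residual SD of 26 to 28 and correlation 0.5 to 0.6, w2 runs from 0.69 to 0.81. The increases are 0.5–0.7%, 2.0–2.8%, 4.5–6.3% and 8.0–11.2% for gaps of 0.1, 0.2, 0.3 and 0.4.

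**Set 2: standardised scale.** All SDs 1, Week 2–Week 8 correlation 0.6, so each slope for change is the correlation with Baseline minus 1. Worked case with Baseline correlations 0.6 and 0.4: S22 = 0.64, S88 = 0.84, S28 = 0.6 − 0.24 = 0.36; w2 = 0.48 / 0.76 = 0.632; (0.632 × 0.2)² / 0.84 = 1.9%.

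| Correlation with Baseline, Week 2 / Week 8 | Slope gap | Variance increase | Equivalent subjects of 462 | 90% power becomes |
|---|---|---|---|---|
| 0.5 / 0.5 | 0 | 0% | 0 | 90.0% |
| 0.6 / 0.5 | 0.1 | 0.4% | 2 | 89.9% |
| 0.6 / 0.4 | 0.2 | 1.9% | 9 | 89.5% |
| 0.6 / 0.3 | 0.3 | 4.7% | 21 | 88.6% |
| 0.7 / 0.3 | 0.4 | 11.6% | 48 | 86.6% |

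Equivalent subjects are 462 × (1 − 1/(1 + increase)). The 90% starting point is illustrative.

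**Sensitivity.** Over a grid of 1,350 combinations of SDs and correlations, the median increase was 0.4%, 1.7% and 4.5% for gaps near 0.1, 0.2 and 0.3. Extreme combinations reached 2.2%, 9.5% and 28%.

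**Simulation check.** REML with unstructured covariance, 308 vs 154, 1,000 trials per scenario, about 6% missing at Week 8.

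- Model-variance ratios (SAP model to model with the extra term) were 0.999, 1.005, 1.022 and 1.126 for gaps of 0, 0.1, 0.2 and 0.4.
- With no true effect and a gap of 0.2, both models rejected in 4.9% of trials. The SAP model's mean standard error (0.0946) matched the empirical one (0.0943).
- With equal slopes, the standard error was 0.0884 without the term and 0.0885 with it.
- With outcome-dependent dropout and a gap of 0.4, the common-slope estimate averaged 0.339 against a true 0.33. The shift is small beside a standard error of 0.103.

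**The case against.** The strongest reply is that nothing here is wrong. A Baseline main effect with treatment-by-visit and unstructured covariance is a complete, prespecified and legitimate MMRM. Any loss depends on slopes that the documents do not describe, and at moderate gaps it is a fraction of a percentage point of power, or little more. IBDQ and FACIT-F are tested only after nine and eleven earlier hypotheses respectively (counting the primary) have succeeded, and nothing indicates that either is close to a power limit. All of that stands, and it limits the point to efficiency.

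Three stronger readings are tempting, and the documents support none of them:

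- **The Week 8 comparison does lose precision, by the equivalent of some 10 to 40 of 462 subjects.** That needs slope gaps of 0.2 to 0.4. Neither document states that change depends more on Baseline at Week 8 than at Week 2, and with equal slopes the loss is zero.
- **The test or confidence interval is invalid.** Under the unstructured covariance the residual variance absorbs the misfit, and the simulated error rate was as intended. The fallback structures were not examined.
- **Every continuous endpoint over time suffers the same loss.** Only two-visit settings were computed, and those other endpoints lie outside multiplicity control.

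Timing is a fair objection too. SAP version 6.0 is dated 19 January 2021 and the last subject was randomized on 26 May 2020 (SAP Appendix D). Changing the model for ranked endpoints is clean only before lock and unblinding.

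**Conclusion.** The point holds as a conditional one. As written, SAP 8.3.2 uses one Baseline slope for Week 2 and Week 8, and this applies to ranked endpoints 9 and 11. If the true slopes differ in either direction, the Week 8 comparison is less precise than the collected data allow. In the cases worked, the variance cost is negligible up to a gap of 0.1, about 2–3% at 0.2, about 5–6% at 0.3, and about 8–12% only at 0.4. These figures rest on assumed SDs and correlations, and extreme combinations give more. They also rest on both scores being collected at Week 2 as well as Week 8; with Week 8 alone there would be no common slope to question. Since the term costs practically nothing when it is not needed, this is a free improvement, for efficiency only.

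**What to change.** In SAP 8.3.2, add the Baseline-by-visit interaction to the MMRM for IBDQ and FACIT-F and, for consistency, for other continuous endpoints with more than one post-baseline visit. Make the change before database lock and unblinding, and record it in the version history (SAP 13.0). If lock has already passed, keep the prespecified model for the ranked tests and report the extended model as a supportive analysis.

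The cost is one parameter per extra visit, so one parameter in about 460 subjects for these two scores. The standard error changes by about 0.1% or less if the slopes are equal. No new data are needed, and neither the estimand nor the testing order changes.

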#### 8.4 Primary Efficacy Endpoint and Analyses

#### 8.4.1 Primary Efficacy Endpoint

The primary efficacy endpoint is the achievement of clinical remission per Adapted Mayo score at Week 8. The primary estimand is the difference in the percentage of subjects achieving clinical remission per Adapted Mayo score at Week 8 regardless of premature discontinuation of study drug and without initiation or dose escalation of UC-related corticosteroids (See Section 8.2.2) in the upadacitinib 45 mg QD and placebo groups in the ITT population. Details of the estimands definition are outlined in Appendix E.

#### 8.4.2 Handling of Missing Data for the Primary Efficacy Endpoint

The NRI-C will be the primary approach for missing data handling in the analyses of the primary efficacy endpoint.

[figure not shown]
The NRI-NC and HMI approaches will be used as sensitivity analyses.

#### 8.4.3 Primary Efficacy Analysis

The primary analysis will compare the proportion of subjects achieving clinical remission in upadacitinib treatment group and placebo group in the ITT1 population. The difference between the treatment groups in the primary efficacy endpoint will be assessed using the CMH test and will be stratified by bio-IR status (bio-IR vs. non-bio-IR), Baseline corticosteroid use (yes vs. no) and Baseline Adapted Mayo score (≤ 7 vs. > 7). A CMH based two-sided 95% confidence interval for the difference between treatment groups will be calculated.

#### 8.4.4 Additional Analyses of the Primary Efficacy Endpoint

For the primary efficacy endpoint, the same CMH analysis as detailed in Section 8.1 will be performed using As Observed (AO) data handling without any imputation as an additional analysis. The analysis will be conducted on the ITT1 population who have the efficacy measurement at Week 8 visit.

For the primary efficacy endpoint, a supplementary analysis will be conducted to evaluate the potential impact of deviations. In this analysis, subjects with deviations that could potentially impact the analysis of primary endpoint will be excluded. The criteria will be fully defined in the classification plan. Exclusion of subjects will be adjudicated by the therapeutic area medical director (TAMD) and reasons for the subjects to be excluded will be documented and finalized before the Induction Study database lock for the primary analysis. Treatment difference between upadacitinib 45 mg QD and placebo with point estimate and 95% CI will be presented using NRI-C approach with the CMH method as detailed in Section 8.1.

#### 8.5 Secondary Efficacy Analyses

[figure not shown]
#### 8.5.1 Key Secondary Efficacy Analyses

The key secondary endpoints are defined in Section 3.2. The estimands corresponding to the secondary efficacy endpoints are defined in Section 2.1. Details of the estimand definitions are outlined in Appendix E. For ITT1 Population, secondary efficacy endpoints in Part 1 will be analyzed by comparing upadacitinib treatment group and placebo group. The binary secondary endpoints will be analyzed by CMH and the corresponding analyses are specified in Section 8.3.1. The NRI-C will be the primary approach for missing data handling in the analyses of binary secondary efficacy endpoints. The NRI-NC approach will be used as sensitivity analyses.

The continuous secondary endpoints will be analyzed by MMRM and the corresponding analyses are specified in Section 8.3.2.

## 8.5.2 Supportive Secondary Efficacy Analyses

The secondary efficacy endpoints will also be analyzed for ITT1 population using As Observed (AO) data handling without any imputation. The categorical endpoints and continuous endpoints will be analyzed by CMH and MMRM, respectively, and the corresponding analyses are specified in Section 8.1.

#### 8.6 Additional Efficacy Analyses

Additional efficacy endpoints are defined in Section 3.3. The estimands corresponding to the additional efficacy endpoints are defined for each of the binary additional endpoints as follows: difference in the percentage of subjects achieving binary endpoints; regardless of premature discontinuation of study drug and without initiation or dose escalation of UCrelated corticosteroids (See Section 8.2.2) in the upadacitinib 45 mg QD and placebo groups in the ITT population. The estimands corresponding to the additional efficacy endpoints are defined for each of the continuous additional endpoints as follows: difference in the mean change from baseline regardless of premature discontinuation of study drug and if subjects would not initiate or escalate dose of UC-related corticosteroids (See Section 8.2.2) in the upadacitinib 45 mg QD and placebo groups in the ITT population. For ITT1 Population, additional efficacy endpoints in Part 1 will be analyzed by comparing upadacitinib treatment group and placebo group. The categorical endpoints and continuous endpoints will be analyzed by CMH and MMRM (or ANCOVA), respectively, and the corresponding analyses are specified in Section 8.3. The NRI-C approach will be used for missing data handling in the analyses of categorical efficacy endpoints.

For ITT2 population, descriptive statistics will be provided for additional efficacy endpoints in Part 2. The NRI-C approach will be used for missing data handling in the analyses of categorical efficacy endpoints.

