#### 3.3 Other Efficacy Endpoints

The following additional efficacy endpoints will be evaluated for Part 1:

[figure not shown]
- The achievement of response in IBDQ Bowel Symptom domain (defined as increase of IBDQ bowel symptom domain score ≥ 6 from Baseline) at Week 8;
- The achievement of response in IBDQ fatigue item (defined as increase of IBDQ fatigue item score ≥ 1 from Baseline) at Week 8;
- The achievement of SFS of 0, RBS of 0 and endoscopic subscore of 0 at Week 8;
- The achievement of SFS of 0, RBS of 0 and endoscopic subscore of ≤ 1 at Week 8;
- The achievement of clinical remission per Full Mayo score at Week 8;
- Change in Full Mayo score from Baseline at Week 8;
- The achievement of clinical remission per Partial Mayo score over time;
- The achievement of clinical response per Partial Adapted Mayo score over time;
- The achievement of clinical response per Partial Mayo score over time;
- The achievement of SFS  $\leq$  1 over time;
- The achievement of RBS of 0 over time;
- The achievement of Fecal calprotectin below 150 mg/kg over time;
- Change from Baseline in fecal calprotectin over time;
- Change from Baseline in hs-CRP over time;
- Change from Baseline in Partial Adapted Mayo score, Partial Mayo score and SFS, RBS over time;
- Change from Baseline in UCEIS score over time;
- Change from Baseline in laboratory and nutritional parameters (e.g., hemoglobin, hematocrit, albumin, total protein concentration, and weight);
- Change from Baseline in subject-reported stool frequency (absolute values) over time;
- Change from Baseline in IBDQ total and domain score over time;
- Change from Baseline in individual IBDQ item under Bowel Symptom domain (for Q1, Q5, Q9, Q13, Q17, Q20, Q22, Q24, Q26, and Q29) over time;

- The achievement of IBDQ response (defined as increase of IBDQ total score
   ≥ 16 from Baseline) over time;
- The achievement of IBDQ remission (defined as IBDQ total score ≥ 170) over time;
- Change from Baseline in EQ-5D-5L score over time;
- Change from Baseline in WPAI scores over time;
- Change from Baseline in SF-36 Physical Component Summary (PCS) and Mental Component Summary (MCS) components and domain scores over time;
- Summary of PGIC improvement category over time;
- Summary of PGIS severity category over time;
- Change from Baseline in FACIT-F score over time;
- Change from Baseline in UC-SQ score over time;
- UC-related hospitalizations through Week 8;
- UC-related surgeries through Week 8;

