- All-cause hospitalizations through Week 8;
- All-cause surgeries through Week 8.

The following additional efficacy endpoints will be evaluated for Part 2:

- The achievement of clinical remission per Adapted Mayo score at Week 16;
- The achievement of endoscopic improvement at Week 16;
- The achievement of endoscopic remission at Week 16;
- The achievement of clinical response per Adapted Mayo score at Week 16;
- The achievement of clinical response per Partial Adapted Mayo score at Week 10;
- The achievement of histologic-endoscopic mucosal improvement at Week 16;
- The achievement of no bowel urgency at Week 16;
- The achievement of no abdominal pain at Week 16;
- The achievement of histologic improvement at Week 16;
- Change from Baseline in IBDQ total score at Week 16;

- The achievement of mucosal healing at Week 16;
- Change from Baseline in FACIT-F score at Week 16.

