#### 8.2.2 UC-Related Corticosteroids

[figure not shown]
The UC-related corticosteroids intercurrent event is defined as follows.

- subjects not on UC-related corticosteroids (systemic or locally acting corticosteroids for UC) at Baseline who initiated UC-related corticosteroids during the Induction Study;
- subjects on UC-related systemic corticosteroids at Baseline who have dosages increased to greater than the prednisone equivalent dose of corticosteroid taken at Baseline, or initiation of any rectal corticosteroids during the Induction Study regardless of rectal corticosteroid dose;
- subjects on UC-related rectal corticosteroids at Baseline who have dosages increased to greater than the dose taken at Baseline, or initiation of any new type of rectal or any systemic corticosteroids during the Induction Study.

The time point of the UC-related corticosteroids intercurrent event is defined as the date when one of the scenarios above occurs for a subject. As such, subjects will be considered as "non-responder" for binary endpoints at or after the occurrence of the UC-related corticosteroids intercurrent event through the end of the Induction Study. For continuous endpoints, all measurements at or after the occurrence of the UC-related corticosteroids intercurrent event through the end of the Induction Study will not be used in the analysis.

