#### 8.3.1 Categorical Endpoints

For binary efficacy endpoints, missing data will be handled using the following approaches:

[figure not shown]
• The primary approach for handling missing data in the analysis of binary endpoints will use Non-Responder Imputation while incorporating Multiple Imputation (MI) to handle missing data due to COVID-19 (NRI-C).

The NRI-C will categorize any subject who does not have an evaluation during a pre-specified visit window (either due to missing assessment or due to early withdrawal from the study) as a non-responder for the visit. The only exception is that missing data due to COVID-19 infection or logistical restrictions related to the COVID-19 pandemic will be handled by Multiple Imputation (MI). At each visit, subjects will be characterized as responders or non-responders based on MI imputed values if missing due to COVID-19; otherwise, subjects will be considered as non-responders for missing due to

other reasons in the NRI-C approach. In addition, at or after the occurrence of the UC-related corticosteroids intercurrent event (see Section 8.2.2), subjects will be counted as non-responders.

- A sensitivity analysis for categorical endpoints will use NRI with No special data handling for missing due to COVID-19 (NRI-NC).
   NRI-NC will be performed in the same way as NRI-C without the exception above. Missing due to COVID-19 infection or logistical restrictions will also be counted as non-responders. Subjects at or after the occurrence of the UC-related corticosteroids intercurrent event will still be counted as non-responders. This is the same method as the "NRI" defined in the protocol.
- Hybrid Multiple Imputation Method (HMI): Sensitivity analysis will be performed using hybrid multiple imputation method for the primary endpoint. Subjects who discontinue study drug prior to Week 8 due to lack of efficacy or AEs and have no available measurements will be considered as "non-responder" for clinical remission. Subjects who discontinue for other reasons and have no available measurements will be categorized according to the data from multiple imputations.

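### SAP 8.6 applies the non-responder rules to hospitalisation and surgery, where the event is unfavourable, and either way of coding them misstates incidence

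*SAP*

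**What the plan says.** SAP 3.3 lists four event outcomes among the other efficacy endpoints for Part 1: "UC-related hospitalizations through Week 8", the matching item for surgeries, "All-cause hospitalizations through Week 8", and all-cause surgeries. Protocol 5.3.3.3 defines all four as proportions of subjects, so they are binary.

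SAP 8.6 gives one estimand for every binary additional endpoint: the difference in the percentage of subjects achieving it, "regardless of premature discontinuation of study drug and without initiation or dose escalation of UCrelated corticosteroids". For missing data it says: "The NRI-C approach will be used for missing data handling in the analyses of categorical efficacy endpoints".

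Two other sections say what that entails:

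- SAP 8.2.2 makes a subject a non-responder "for binary endpoints at or after the occurrence of the UC-related corticosteroids intercurrent event through the end of the Induction Study". The first trigger is "subjects not on UC-related corticosteroids (systemic or locally acting corticosteroids for UC) at Baseline who initiated UC-related corticosteroids during the Induction Study"; dose increases and new steroid types also count.
- SAP 8.3.1 builds the same rule into NRI-C: "at or after the occurrence of the UC-related corticosteroids intercurrent event (see Section 8.2.2), subjects will be counted as non-responders". NRI-C also makes a non-responder of "any subject who does not have an evaluation during a pre-specified visit window", unless the gap is due to COVID-19, in which case the value is multiply imputed.

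Protocol 8.1.3 words the steroid rule differently: for categorical efficacy endpoints the subject is a failure.

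**The concern.** For remission or response, 'non-responder', 'endpoint not achieved' and 'failure' all describe the same bad result. For a hospital admission or an operation they do not. Not achieving the endpoint is the good result, and failure is the bad one. The SAP never says which is meant for these four endpoints, so two programmers could follow the text and code the same subject in opposite ways.

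Hospitalisation and surgery matter directly to patients, and SAP 12.0 has the additional endpoints analysed at a nominal two-sided 0.05. A between-arm comparison will therefore be produced, from a rule that does not measure incidence under either coding.

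**Working it through.** **1. Are the four endpoints inside the rule?** They are listed as efficacy endpoints (SAP 3.3) and are binary (protocol 5.3.3.3). SAP 8.6 covers each binary additional endpoint. SAP 8.2.2, 8.3.1, 8.6 and Appendices D and E contain no exemption.

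**2. Does the rule act on observed data?** Yes. SAP 8.3.1 sets measurements at or after the steroid event to missing before imputation, then imposes non-response whatever value was imputed. Such events can be on record: protocol 5.4.1 asks subjects who stop study drug to remain in follow-up, and SAP 8.2.1 uses their data. Protocol 5.2.3.3 prohibits starting rectal or systemic steroids during induction but refers such cases for discussion, without automatic removal.

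**3. What happens to each type of subject?** Coding A takes non-responder as endpoint not achieved (SAP 8.6 wording). Coding B takes it as failure (protocol 8.1.3 wording), extended to missing data.

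| Subject, through Week 8 | On record | Coding A | Coding B |
|---|---|---|---|
| Admitted, no steroid start | event | event | event |
| Admitted at or after steroid start | event | no event | event |
| Admitted before steroid start | event | unclear | event |
| Never admitted, steroid start | no event | no event | event |
| No admission on record, evaluation missing (not COVID-19) | no event | no event | event |

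The third row is unclear under A because the plan has no date convention for a cumulative endpoint. Judged on the admission date, the event stands; judged as a status at Week 8, after the steroid date, it is lost.

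**4. Size.** The plan states no figure for these endpoints, so there is none to reproduce. The arm sizes, 154 and 308, come from SAP 2.4. Everything else is assumed:

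- h, the true proportion with the event: 5% placebo (0.05 × 154 = 7.7 subjects) and 2% upadacitinib (0.02 × 308 = 6.2). True difference: 2 - 5 = -3.0 points.
- s, the share of admitted subjects whose admission falls at or after a steroid start: 25% to 100%.
- o, the proportion starting steroids without admission: 5% placebo, 1% upadacitinib.

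Coding A reports h × (1 - s):

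| s, both arms | Placebo | Upadacitinib | Difference (points) |
|---|---|---|---|
| 25% | 5 × 0.75 = 3.75% | 2 × 0.75 = 1.5% | -2.25 |
| 50% | 2.5% | 1.0% | -1.5 |
| 75% | 1.25% | 0.5% | -0.75 |
| 90% | 0.5% | 0.2% | -0.3 |
| 100% | 0% | 0% | 0 |

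If s differs by arm, the result can move either way. With 90% placebo and 50% upadacitinib: 5 × 0.10 = 0.5% against 2 × 0.50 = 1.0%, or +0.5 points. With 50% and 90%: 2.5% against 0.2%, or -2.3 points.

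Coding B reports h + o: 5 + 5 = 10% against 2 + 1 = 3%, or -7.0 points. Missing evaluations would add further false events.

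Other assumed true rates, same s and o:

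| True rates | True difference | Coding A | Coding B |
|---|---|---|---|
| 3% and 1% | -2.0 | -1.5 to 0 | 2 - 8 = -6.0 |
| 8% and 4% | -4.0 | -3.0 to 0 | 5 - 13 = -8.0 |

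**5. Is there an uncorrected version elsewhere?** As-observed analyses are assigned to the primary endpoint (SAP 8.4.4) and the secondary endpoints (SAP 8.5.2). The supplementary analysis in Appendix E covers the primary and key binary secondary endpoints. None is assigned to the SAP 3.3 list.

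**The case against.** The strongest reply is that the rule was never meant for these endpoints. The response endpoints in SAP 3.3 are phrased as achievements; these four are not. NRI-C is built on evaluations at visits, whereas admissions and operations are collected as events on a supplemental form (protocol Appendices C and E). Table D-1 gives no NRI-C seed for them. All this suggests that imputation was not intended. It is not an exemption, though: the steroid override and plain non-responder imputation need no seed, and SAP 8.6 speaks of each binary additional endpoint.

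Second, the events do not vanish from reporting. Admission makes an adverse event serious (protocol 6.1.1.2). SAEs are tabulated and listed (SAP 9.2.5), and serious TEAEs are compared between arms (SAP 9.2.2). This stands and limits the harm. But those tables do not give the proportion per arm hospitalised or operated on for UC.

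Third, a reader might infer that observed admissions will certainly be erased. The documents do not support that. It requires coding A and an event at or after the steroid date; under the protocol's failure wording no observed admission is lost. A reader might also infer a known direction of bias, with steroid starts and dropouts more frequent on placebo. Nothing in the documents establishes this, and the sign change in the working comes only from an assumed 90% against 50%.

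Finally, a simple observed proportion also counts an early withdrawal as event-free. That is fair, and the remedy has to address it.

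**Conclusion.** The point holds as a defect in a stated rule. NRI-C and the steroid rule cover hospitalisation and surgery, and neither available meaning of non-responder yields the incidence of these events. Coding A can remove real events; coding B creates false ones. Which would occur cannot be settled from the text.

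The size is illustrative only. Against an assumed true difference of -3.0 points, coding A reports between -2.25 and 0 with equal steroid use by arm, and coding B about -7. The direction and amount depend on rates that the documents do not give.

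Severity is low. The four endpoints are exploratory and outside the fixed testing sequence of SAP 12.0. The primary endpoint, the ranked secondary endpoints, the sample size and type I error control are untouched.

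**What to change.** Add one sentence to SAP 8.6: NRI-C and the corticosteroid override do not apply to the four hospitalisation and surgery endpoints; all recorded events through Week 8 count, whatever the steroid use or study drug discontinuation, and are reported as observed proportions by arm, with exposure-adjusted rates to account for early withdrawal.

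This settles both the coding direction and the date question. It needs no new data, since the events are already collected, and little programming. It is best made before treatment codes are released for analysis.
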